5.5 System Check: Meter Control Tests

All the meters will be tested using control solutions, Level A and B of CareSens Pro control solution for the glucose and level A and level B of KetoSens control solution for the β -ketone at the beginning and end of each study day and the results will be recorded. If the results are out of range, troubleshooting will be performed (see the user's manual) and the test will be repeated (a total of three (3) attempts per control test are allowed). If the QC results are out of range after troubleshooting is complete, the meter will be removed from the study. The meters who failed control solution testing and were removed from the study will be reported. This will be documented on the Device Deficiency Form.

5.6 Operation of YSI Glucose Analyzer

5.6.1 YSI Control Tests

The YSI Analyzer auto calibrates every 5 samples or 15 minutes, whichever comes first. If the YSI fails to calibrate correctly, the trained study staff will troubleshoot the system and perform a new calibration. The glucose results for the blood samples analyzed previous to the failed calibration will be rejected.

For quality control testing on YSI Analyzer, the YSI control solutions and the 180 (2747) standard will be run at the beginning and end of the study day or at any time the YSI needs to be restarted. Each quality control solution is required to be within its stated range and 180 (2747) standard in order to continue to use the analyzer in the study. In addition, the calibration shift should not have a difference of more than 2% and the probe current should be less than 6 nA before using the YSI Analyzer. If not, the trained study staff/technician will troubleshoot the analyzer and repeat the quality control testing. If quality control solution testing continues to fall out of range, the glucose concentration values for the blood samples analyzed previous to the failed control solution results will be rejected.

The YSI will be maintained and operated according to the instructions in the manufacturer's operating manual. The YSI will be set up and appropriate maintenance performed before the study begins. The YSI clock will be set to 24-hour format using an accurate time device (such as site central clock or atomic clock).

	Method Comparison/User Evaluation of the i-SENS Self-Monitoring Blood Glucose / β-Ketone System(CareSens PRO GK BT)	Document No. BGM-2205084
	Authorized approval of controlled documents is required for external release.  Controlled Document  Uncontrolled Document	Version No. 2

Trained study staff will keep a maintenance log, including daily operational checks, maintenance, and membrane changes.

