5.6.2 Glucose Testing of Subject Plasma Samples

YSI 2747 standard is run before each subject sample cycle, and it needs to be within the acceptable range.

The subject capillary plasma samples will be tested in duplicate. If the average of replicates 1&2 do not fall within range (within 4% for readings above 100mg/dL or 4 mg/dL for samples less than or equal to 100mg/dL) the sample will be run a third time and the 2 average replicate readings that fall within range (4% for readings above 100mg/dL or 4 mg/dL for samples less than or equal to 100mg/dL) will be recorded as evaluable.

In general, duplicates will be averaged for each subject. If the sample is insufficient or missing and have only a single YSI value, it will be used as the YSI determination. If none of the 3 average replicates fall within (4% for readings above 100mg/dL or 4 mg/dL for samples less than or equal to 100mg/dL) will be recorded as non-evaluable. If the YSI autocals between subject sample duplicates, then another YSI 2747 standard will be run before completing the subject sample cycle.

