5.7 Operation of Rx Imola β -ketone Measurement

5.7.1 Rx Imola Control

Rx Imola ketone analyzer will be calibrated using Ranbut, Ranbut Cal and distilled water at least once a week. Ranbut is prepared by putting 10 ml of R1a solution in R1b container. The solution can be used for one week after preparation. If FAIL is displayed during calibration, the trained study staff/technician will troubleshoot the system and perform a new calibration. If calibration continues to fail, reproduce the Ranbut solution and perform a new calibration. Rx Imola will also be calibrated when QC is failed or Ranbut used for sample measurements is replaced.

For quality control testing on Rx Imola analyzer, QC lv 2 and QC lv 3 of Rx control solution will be run at the beginning and end of the study or at any time the Rx Imola needs to be restarted. Each quality control solution is required to be within its stated range in order to continue to use the analyzer in the study. If quality control solution testing continues to fall out of range, the β -ketone concentration values for the blood samples analyzed previous to the failed control solution results will be rejected.

The Rx Imola will be maintained and operated according to the instructions in the manufacturer's operating manual. The Rx Imola will be set up and appropriate maintenance performed before the study begins.

Trained study staff will keep a maintenance log, including daily operational checks, maintenance, and calibration solution changes.

5.7.2 β -ketone Testing of Subject Plasma Samples

The subject capillary plasma sample will be tested in duplicate using Rx Imola analyzer. If the measured values differ by > 0.075 mmol/L at ketone < 1.5 mmol/L or $> 5\%$ at ketone ≥ 1.5 mmol/L, the sample will be run a third time and the 2 average replicate readings that fall within range will be recorded as evaluable. In general, duplicates will be averaged for each subject. If the sample is insufficient or missing and has only a single Rx Imola value, it will be used as the Rx Imola determination. If none of the 3

	Method Comparison/User Evaluation of the i-SENS Self-Monitoring Blood Glucose / β-Ketone System(CareSens PRO GK BT)	Document No. BGM-2205084
	Authorized approval of controlled documents is required for external release.  Controlled Document /  Uncontrolled Document	Version No. 2

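### Comparator values obtained before a failed control check are rejected only if the check keeps failing, so values preceding a successful correction stay in by default; the gap is widest for Rx Imola.

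*Combined protocol and SAP*

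**What the plan says.** Section 5.6.1 gives two rules for the YSI.

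- **Failed calibration.** Staff troubleshoot and recalibrate, and "The glucose results for the blood samples analyzed previous to the failed calibration will be rejected". Nothing further has to happen first.
- **Failed control solution.** Controls "will be run at the beginning and end of the study day or at any time the YSI needs to be restarted". For continued use, "Each quality control solution is required to be within its stated range and 180 (2747) standard in order to continue to use the analyzer". The next step is "If not, the trained study staff/technician will troubleshoot the analyzer and repeat the quality control testing". Rejection comes only after that: "If quality control solution testing continues to fall out of range, the glucose concentration values for the blood samples analyzed previous to" the failed control are dropped.

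Section 5.7.1 repeats the second pattern for Rx Imola: "If quality control solution testing continues to fall out of range, the β -ketone concentration values" from before the failure are rejected. It also says "Rx Imola will also be calibrated when QC is failed or Ranbut used for sample measurements is replaced". Rx Imola controls are scheduled at the start and end of the study, not of the day, or at a restart. Calibration is at least weekly.

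For glucose only, section 5.6.2 adds: "YSI 2747 standard is run before each subject sample cycle, and it needs to be within the acceptable range". Section 5.6.1 has the YSI autocalibrate every 5 samples or 15 minutes.

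The non-evaluability reasons in 5.8.3 do not include a failed comparator control. Note 2 in 4.3 keeps the evaluable data of every eligible subject.

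**The concern.** A control that passes after recalibration, or after a membrane or reagent change, shows that the analyzer works in its new state. It does not vouch for values produced in the old state. The persistence condition nevertheless lets a pass after correction settle the matter for the earlier values. The calibration rule in the same section treats comparable evidence the opposite way.

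Every accuracy criterion in section 9 takes the comparator as its reference. A comparator fault that affects a run of consecutive subjects moves all their differences in the same direction. The duplicate limits in 5.6.2 and 5.7.2 detect imprecision between replicates, not a shift common to both.

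**Working it through.** **1. What happens to earlier values, event by event**

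- YSI calibration fails: rejected, with no further condition (5.6.1).
- YSI control fails and still fails on repeat: rejected (5.6.1).
- YSI control fails and passes after troubleshooting: no rule in 5.6.1; not a reason in 5.8.3; retained under 4.3 Note 2.
- Rx Imola control fails and still fails: rejected (5.7.1).
- Rx Imola control fails and passes after recalibration: no rule in 5.7.1; not a reason in 5.8.3; retained under 4.3 Note 2.

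A failure at the opening YSI check precedes that day's samples, so the exposure is at closing and restart checks. Read strictly, the troubleshooting sentence in 5.6.1 follows the limits on calibration shift and probe current. I take it to cover the controls too, since the next sentence speaks of control testing that continues to fail.

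**2. How many misses the glucose criteria allow**

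The plan states no figure on this point, so there is none to reproduce. With the minimum n = 350 (section 3) and the section 9 criteria:

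- 0.95 × 350 = 332.5, so 333 must be within ±15% and 17 may miss.
- 0.99 × 350 = 346.5, so 347 must be within ±20% and 3 may miss.

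**3. Effect of a retained shifted run**

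Assumptions, none of them in the documents: normal relative meter error with SD 6%, no meter bias, and 30 of 350 pairs affected by a comparator shift s that adds to the difference.

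Miss probability: p(s, L) = 1 − Φ((L − s)/6) + Φ((−L − s)/6), with s and L in percent.

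- Unshifted: p(0, 15) = 0.0124; p(0, 20) = 0.00086.
- 8% shift: p(8, 15) = 0.122; p(8, 20) = 0.0228.
- 10% shift: p(10, 15) = 0.202; p(10, 20) = 0.0478.

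Expected misses = 320 × p(0, L) + 30 × p(s, L). The chance of passing is P(X + Y ≤ 17) or P(X + Y ≤ 3), with X ~ Bin(320, p(0, L)) and Y ~ Bin(30, p(s, L)).

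| Shift | Misses beyond ±15% | Pass | Misses beyond ±20% | Pass |
|---|---|---|---|---|
| 0 | 4.3 | 1.000 | 0.30 | 1.000 |
| 8% | 3.97 + 3.65 = 7.6 | 0.999 | 0.27 + 0.68 = 0.96 | 0.984 |
| 10% | 3.97 + 6.07 = 10.0 | 0.991 | 0.27 + 1.43 = 1.7 | 0.910 |

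Sensitivity to direction: if the comparator reads the true value times (1 + b), the meter misses when its relative error falls outside (1 ± L)(1 + b) − 1. For the 30 affected pairs, b = −10% gives 8.4 misses beyond ±15% and 2.7 beyond ±20%; the same pass formula then gives 0.94 and 0.64. For b = +10% the misses are 4.2 and 0.7, and the pass chances 0.999 and 0.98. The 0.91 in the table lies between the two directions.

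**4. Could such a run hide a meter bias?**

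A meter reading 10% high misses ±15% with probability p(10, 15) = 0.202. The 320 unaffected pairs alone give 320 × 0.202 ≈ 65 misses against 17 allowed. The study fails whatever happens in the other 30.

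**5. Ketone**

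At or above 1.5 mmol/L, with an assumed SD of 7% and a 15% comparator shift, the miss rate beyond ±20% is 1 − Φ(5/7) = 24%, against 0.4% unshifted. Section 3 requires only 10 such samples, so if all 10 were affected this is about 2.4 misses. Below 1.5 mmol/L the limit is ±0.3 mmol/L, and a 15% shift at, say, 0.3 mmol/L is only 0.15 × 0.3 = 0.045 mmol/L.

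**The case against.** The strongest reply is that glucose is already protected. Thirty subjects in duplicate make about 60 readings, hence at least 60/5 = 12 autocalibrations and 30 in-range standards. A uniform shift of 8 to 10% running unnoticed through all of that is hard to credit. This stands. It confines the YSI gap chiefly to faults that the 2747 standard does not detect, for example at another glucose level; the documents do not give the standard's acceptable range.

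Second, the protocol speaks of troubleshooting, not repair. A first failure may come from the control material or its handling, in which case the earlier values are sound. That also stands, but no finding of cause is required before the values are kept.

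Third, retention is inferred. A reader might conclude that the protocol orders faulty values to be kept; it does not say so. The inference rests on silence together with 5.8.3 and 4.3 Note 2. Section 10 does allow spurious or unused data to be noted with reasons, but it gives no criterion, so any exclusion would be decided case by case.

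None of this covers Rx Imola. No per-sample standard is described there, and a closing control at the end of the study could fail, pass after recalibration, and leave a long run of ketone values standing.

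**Conclusion.** The concern holds as a gap in the rejection rule and an inconsistency with the calibration rule in the same section. It should be closed before data collection.

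Its likely effect on the glucose verdict is modest. Under the stated assumptions the chance of meeting the ±20% criterion falls from about 1.00 to 0.98 (8% shift) or 0.91 (10% shift), and the ±15% criterion is barely affected. The SD, shift and run length are all assumed. The figures show that a few retained values can matter, not that a fault will occur.

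Two stronger readings are tempting and not supported. One is that a retained run could let a biased meter pass: at 30 subjects it cannot hide a 10% bias. The other is that the 24% ketone miss rate endangers the ketone criterion. About 2.4 misses is small against 17 if the 95% is pooled over 350 results. It would be serious only if the criterion applied separately to the 10 high samples, and section 9 does not settle that.

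The case is strongest for Rx Imola, because of its sparse control schedule and weekly calibration.

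**What to change.** In 5.6.1 and 5.7.1, replace the persistence condition with wording such as:

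> If a control is out of range, it is repeated once with nothing changed on the analyzer. If the repeat is in range, earlier values stand. If corrective action on the analyzer is needed, subject values obtained since the last passing control check are rejected, or the stored plasma is re-run on the corrected analyzer if still within the 5.8.3 time limit, unless a documented cause shows that the control material and not the analyzer was at fault.

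Add this reason to the list in 5.8.3. Run the Rx Imola controls at the beginning and end of each study day, as for YSI. Without that, the last passing check could be the one at study start, and a single late failure could discard every ketone value.

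State also that the two-hour limit in 5.8.3 governs a re-run, because 5.4 sets 35 minutes from the meter result. At a closing check most plasma will already be past two hours, so re-running will rescue few samples.

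Cost: a short text change, a few more control runs, and the loss of up to one day's pairs when an analyzer needs correction. Section 3 already allows glucose enrolment to exceed 350.

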5.6.2 Glucose Testing of Subject Plasma Samples

YSI 2747 standard is run before each subject sample cycle, and it needs to be within the acceptable range.

The subject capillary plasma samples will be tested in duplicate. If the average of replicates 1&2 do not fall within range (within 4% for readings above 100mg/dL or 4 mg/dL for samples less than or equal to 100mg/dL) the sample will be run a third time and the 2 average replicate readings that fall within range (4% for readings above 100mg/dL or 4 mg/dL for samples less than or equal to 100mg/dL) will be recorded as evaluable.

In general, duplicates will be averaged for each subject. If the sample is insufficient or missing and have only a single YSI value, it will be used as the YSI determination. If none of the 3 average replicates fall within (4% for readings above 100mg/dL or 4 mg/dL for samples less than or equal to 100mg/dL) will be recorded as non-evaluable. If the YSI autocals between subject sample duplicates, then another YSI 2747 standard will be run before completing the subject sample cycle.

5.7 Operation of Rx Imola β -ketone Measurement

5.7.1 Rx Imola Control

Rx Imola ketone analyzer will be calibrated using Ranbut, Ranbut Cal and distilled water at least once a week. Ranbut is prepared by putting 10 ml of R1a solution in R1b container. The solution can be used for one week after preparation. If FAIL is displayed during calibration, the trained study staff/technician will troubleshoot the system and perform a new calibration. If calibration continues to fail, reproduce the Ranbut solution and perform a new calibration. Rx Imola will also be calibrated when QC is failed or Ranbut used for sample measurements is replaced.

For quality control testing on Rx Imola analyzer, QC lv 2 and QC lv 3 of Rx control solution will be run at the beginning and end of the study or at any time the Rx Imola needs to be restarted. Each quality control solution is required to be within its stated range in order to continue to use the analyzer in the study. If quality control solution testing continues to fall out of range, the β -ketone concentration values for the blood samples analyzed previous to the failed control solution results will be rejected.

The Rx Imola will be maintained and operated according to the instructions in the manufacturer's operating manual. The Rx Imola will be set up and appropriate maintenance performed before the study begins.

Trained study staff will keep a maintenance log, including daily operational checks, maintenance, and calibration solution changes.

5.7.2 β -ketone Testing of Subject Plasma Samples

The subject capillary plasma sample will be tested in duplicate using Rx Imola analyzer. If the measured values differ by > 0.075 mmol/L at ketone < 1.5 mmol/L or $> 5\%$ at ketone ≥ 1.5 mmol/L, the sample will be run a third time and the 2 average replicate readings that fall within range will be recorded as evaluable. In general, duplicates will be averaged for each subject. If the sample is insufficient or missing and has only a single Rx Imola value, it will be used as the Rx Imola determination. If none of the 3

	Method Comparison/User Evaluation of the i-SENS Self-Monitoring Blood Glucose / β-Ketone System(CareSens PRO GK BT)	Document No. BGM-2205084
	Authorized approval of controlled documents is required for external release.  Controlled Document /  Uncontrolled Document	Version No. 2

average replicates fall within > 0.075 mmol/L at ketone < 1.5 mmol/L or $> 5\%$ at ketone ≥ 1.5 mmol/L for readings, it will be recorded as non-evaluable.

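### Ketone reference analyzer controls are scheduled per study instead of per study day, and the rejection rules for both analyzers give no look-back start point

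*Combined protocol and SAP*

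**What the plan says.** For the ketone comparator, section 5.7.1 states that two control levels "will be run at the beginning and end of the study or at any time the Rx Imola needs to be restarted". For the glucose comparator, section 5.6.1 states that the controls and the 180 standard "will be run at the beginning and end of the study day or at any time the YSI needs to be restarted". Sections 5.3.2 and 5.5 put the meter controls at the start and close of every study day.

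Section 5.7.1 makes continued use conditional: "Each quality control solution is required to be within its stated range in order to continue to use the analyzer in the study". If controls stay out of range, the "concentration values for the blood samples analyzed previous to the failed control solution results will be rejected". Section 5.6.1 has the same rule for YSI controls, and for YSI calibration it says: "The glucose results for the blood samples analyzed previous to the failed calibration will be rejected".

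The other Rx Imola safeguards in 5.7.1 are:
- calibration at least weekly;
- further calibration on two triggers: "Rx Imola will also be calibrated when QC is failed or Ranbut used for sample measurements is replaced";
- the manual: "The Rx Imola will be maintained and operated according to the instructions in the manufacturer's operating manual";
- a log: "Trained study staff will keep a maintenance log, including daily operational checks, maintenance, and calibration solution changes".

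**The concern.** The Rx Imola value is the reference for every ketone accuracy figure, including the 95% acceptance criterion in section 9. If the analyzer shifts and no control is run, a sound meter can look inaccurate, or a meter bias in the same direction can be hidden. As worded, the schedule allows a site to comply fully and run no control solution between the first and last day.

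The rejection rules raise a second question. They say that samples measured before a failure are removed but not how far back removal goes. The set of rejected values is then settled by interpretation, possibly after the results are known.

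**Working it through.** **1. Schedules side by side**

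| Instrument | Scheduled controls | Other stated checks |
|---|---|---|
| Meters (5.3.2, 5.5) | start and close of each study day | on suspicion of malfunction |
| YSI (5.6.1, 5.6.2) | start and close of the study day; restart | autocalibration every 5 samples or 15 minutes; 2747 standard before each subject cycle |
| Rx Imola (5.7.1, 5.7.2) | start and close of the study; restart | calibration at least weekly, on failed QC and on Ranbut replacement; daily operational checks of unstated content |

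Recalibration after a failed control can be triggered only when a control is run. The duplicate rule in 5.7.2 compares the two replicates with each other, so a shift common to both passes.

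**2. Scheduled control occasions between study start and end**

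The number of study days D is not given; assume 5, 20 or 35. As written, with no restart, the count is 0. With daily controls it is 2D − 2 = 8, 38, 68.

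**3. Values exposed to a persistent failure at the final control**

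Input: N = 350 (section 3 minimum), even enrolment assumed.
- Schedule as written, no restart: the last in-range control is the one at study start. The literal reading and a reading limited to the last in-range control reject the same values, all 350.
- Daily controls, look-back to the last in-range control: about N/D = 350/5, 350/20, 350/35 = 70, 17.5, 10.
- Daily controls, literal rule with no start point: a failure at the end of the last day again reaches all 350.

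The figure of 350 under the present text therefore comes from the schedule. The missing start point matters for the YSI now, and for the Rx Imola once a restart occurs or daily controls are adopted.

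**4. YSI calibration**

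If each replicate counts as one sample, 350 × 2 = 700 readings imply at least 700/5 = 140 autocalibrations. Look-back to the last successful one covers at most 5 readings; the literal rule covers every earlier reading in the study.

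**5. Illustration of a reference shift**

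Assume ketone below 1.5 mmol/L, no meter bias, normal meter error with SD s, and a reference shift d. The share within ±0.3 mmol/L is P(d) = Φ((0.3 − d)/s) − Φ((−0.3 − d)/s). With half the pairs shifted, the share is [P(0) + P(d)]/2.

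| s (mmol/L) | P(0) | P(0.10) | half shifted by 0.10 | P(0.15) | half shifted by 0.15 |
|---|---|---|---|---|---|
| 0.10 | 99.7% | 97.7% | 98.7% | 93.3% | 96.5% |
| 0.12 | 98.8% | 95.2% | 97.0% | 89.4% | 94.1% |
| 0.14 | 96.8% | 92.1% | 94.5% | 85.7% | 91.3% |

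The SD, the shift and the share affected are all assumptions. Half of 5, 20 or 35 days is 2.5, 10 or 17.5 days, so at the two longer durations the shift would have to survive at least one or two weekly calibrations.

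**The case against.** The Rx Imola sentence follows the YSI sentence almost word for word, so this is probably a slip and not a design decision. A site may run daily controls anyway, and the manufacturer's manual, which 5.7.1 requires staff to follow, may call for them. Both points are fair, and they rule out calling the comparator uncontrolled. They do not settle the matter: the manual is not in the documents, and 5.7.1 is the operative instruction.

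A reader might infer from the shift table that daily controls would catch such a shift. The documents do not support that. Controls need only fall within their stated range, and neither that range nor the control concentrations are given, so detection of a 0.10 or 0.15 mmol/L shift is not shown.

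A reader might also take the 350 as the size of the look-back gap or as a likely loss. It is neither. It follows from the schedule, needs a persistent failure at the closing control, and no failure probability can be derived.

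On look-back, stopping at the last in-range control is the natural reading, because an in-range control is what permits continued use. The YSI's frequent calibration and per-cycle standard also suggest a short window. That stands as a sensible reading, but the text does not state it.

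Finally, one might argue that the absence of these rejections from section 5.8.3 lets removals go unseen. It does not. They are stated in 5.6.1 and 5.7.1; 5.8.3 also omits replicate disagreement, which 5.6.2 and 5.7.2 make non-evaluable; and section 10 requires unused data to be noted with reasons. That makes removals visible but does not fix the look-back in advance.

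**Conclusion.** The point holds as a wording defect in an operative rule, and it should be corrected. Absent a restart, section 5.7.1 schedules no control-solution check of the ketone comparator between study start and study end, and none of the other stated safeguards amounts to one. At worst, a persistent failure at the closing control leaves all of the minimum 350 ketone values open to rejection, even under the narrower look-back. With daily controls and a defined look-back the exposure is about 70, 17.5 or 10 values, assuming 5, 20 or 35 study days and even enrolment. The open-ended rejection rules are a separate and smaller gap that affects both analyzers. Nothing here shows that the comparator drifted or that the ketone result is wrong.

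**What to change.** 1. In 5.7.1, schedule the Rx Imola controls for the start and close of each study day, and keep the restart controls.
2. In 5.6.1 and 5.7.1, limit rejection after a QC failure to samples analyzed since the last in-range QC run. In 5.6.1, limit rejection after a failed calibration to samples since the last successful calibration. The shorter calibration window should not be applied to QC failures.

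Listing these rejections in 5.8.3 would be optional tidying.

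Cost: 2 levels × 2 occasions = 4 control measurements per study day, so 4D = 20, 80 or 140 over an assumed 5, 20 or 35 days. Against the 4 now scheduled, that is 16, 76 or 136 extra, beside at least 350 × 2 = 700 duplicate subject measurements. The rest is wording.
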